9.5 Physical Examination Data

By-subject listings will be provided for physical examination findings.

Body weight and BMI collected at scheduled visits will be mapped to the weeks per specification in Table 5.2-2. Potentially clinically relevant changes in body weight will be summarized by treatment group and/or by week.

In addition, change from baseline in body weight and percentage of change from baseline in body weight will be analyzed similarly using MMRM model including treatment group, trial center, visit week, and an interaction term of treatment by visit week as fixed effect terms, and interaction term of baseline weight by week as covariates. Change from baseline in body weight percentage of change from baseline in body weight at all mapped visits and last visit will also be explored using ANCOVA model, including treatment and trial center as fixed factors and baseline weight as covariate.

Change from baseline in BMI will be summarized by treatment group and week. In addition, frequencies and percentage of subjects will be provided for classification of BMI by treatment group and week. Shift table will be provided as needed.

9.6 Electrocardiogram Data

For the analysis of QT and QTc, data from three consecutive complexes (representing three consecutive heart beats) will be measured to determine average values. The following QT corrections will be used for reporting purposes:

- QTcF is the length of the QT interval corrected for heart rate by the Fridericia formula: QTcF=QT/(RR)^{0.33}
- QTcN is the length of the QT interval corrected for heart rate by the FDA Neuropharm Division formula: QTcN=QT/(RR)^{0.37}

Potentially clinically relevant changes in the 12-lead ECG identified for the safety analysis set will be listed and summarized by treatment group. Criteria for identifying ECG measurements of potential clinical relevance are provided in Appendix 3.

Categorical changes in ECG parameters will be summarized by treatment group based on the following criteria in Table 9.6-1.

Table 9.6-1	Categorical Change Criteria in QT/QTc Parameters		
Classification	Category	Criteria	
QT	New Onset (> 450 msec)	New onset (>450 msec) in QT means a subject who attains a value > 450 msec during treatment period but not at baseline.	
QTc *	New Onset (> 450 msec)	New onset (> 450 msec) in QTc means a subject who attains a value > 450 msec during treatment period but not at baseline.	
	New Onset (> 450 msec) And > 10% Increase	New onset (> 450 msec) and > 10% increase in QTc means a subject who attains a value > 450 msec and > 10% increase during treatment period but not at baseline	
	New Onset (> 500 msec)	New onset (> 500 msec) in QTc means a subject who attains a value > 500 msec during treatment period but not at baseline.	
	Increase 30 - 60 msec	ase 30 - 60 msec Increase from baseline value $>$ 30 and \le 60 msec in QTc	
	Increase > 60 msec	Increase from baseline value > 60 msec in QTc	

^{*} QTc categorical change criteria apply to QTcF and QTcN.

Summary statistics of changes in ECG parameters will be provided by treatment group and scheduled visit. If ECG assessments are repeated for the same trial visit, the last repeated values will be used for generation of mean change from baseline. This is accomplished by sorting subject data by visit date and visit time (if applicable) within the same trial visit.

9.7 Suicidality

Suicidality is assessed based on C-SSRS data. The "Baseline" version of the C-SSRS is completed at screening and the "Since Last Visit" version is completed at all other specified visits (including ET, if applicable). Baseline of C-SSRS data is defined as the last evaluable assessment prior to first IMP. Descriptive statistics of the incidence of suicidality and incidence of suicidality by type (suicidal behavior and suicidal ideation) is reported by treatment group.

Baseline and Since Last Visit C-SSRS data is summarized to report the incidence of suicidality; suicidal behavior only, emergence of suicidal behavior; suicidal ideation only, emergence of suicidal ideation, emergence of serious suicidal ideation, and worsening of suicidal ideation at trial visits and last visit in addition to overall during the double-blinded period.

Suicidality is defined as reporting any suicidal ideation or behavior. Suicidal behavior only is defined as reporting any type of suicidal behaviors (actual attempt, interrupted attempt, aborted attempt and preparatory acts or behavior) throughout assessment period. Emergence of suicidal behavior is defined as having no suicidal behavior at baseline and reporting any type of behavior at post-baseline.

Suicidal ideation only is defined as reporting any type of suicidal ideation (wish to be dead, non-specific active suicidal thoughts, active suicidal ideation with any methods, active suicidal ideation with some intent and active suicidal ideation with specific plan,). Emergence of suicidal ideation is defined as having no suicidal ideation at baseline and reporting any type of ideation during treatment. Emergence of serious suicidal ideation is defined as having no suicidal ideation at baseline and reporting serious suicidal ideation with score of 4 or 5 on suicidal ideation severity rating during the treatment. Worsening of suicidal ideation is defined as having more severe in most severe suicidal ideation rating at post baseline than at baseline. Numbers of subjects reporting suicidal behavior are also reported by type of suicidal behavior.

Listings for treatment-emergent suicidal behavior, suicidal ideation, serious suicidal ideation and worsening of suicidal ideation will also be provided.

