14.	A positive alcohol test (via breathalyzer, blood, or urine), a positive drug screen for illicit drugs (excluding marijuana) at screening or baseline. NOTE: Subjects who test positive for marijuana at screening may be enrolled if they have no evidence of a substance use disorder, if they agree to refrain from use for the duration of the trial, and if they test negative prior to the baseline visit.
15.	 Any of the following: A significant risk of committing suicide based on history and the investigator's clinical judgment, or routine psychiatric status examination
	Current suicidal behavior
	Imminent risk of injury to self
	• Active suicidal ideation as it is evidenced by an answer of "yes" on Questions 4 or 5 (over the last 6 months) on the suicidal ideation section of the Baseline/Screening version of the C-SSRS
	Any lifetime history of suicidal behavior detected by the Baseline/Screening version of the C-SSRS.

Tabl	e 5.2.2-1 Exclusion Criteria
16.	Any other medical or physical condition(s) that, in the opinion of the investigator, may prevent the subject from completing the trial or would go against the subject's best interest with participation in the trial. This would include any significant illness or unstable medical condition that could lead to difficulty complying with the protocol.
17.	The following laboratory test and ECG results are exclusionary:
	1) Platelets $\leq 75,000/\text{mm}^3$
	2) Hemoglobin ≤ 9 g/dL
	3) Neutrophils, absolute $\leq 1000/\text{mm}^3$
	4) AST > 2 × upper limit of normal
	5) ALT > 2 × upper limit of normal
	6) Creatinine ≥ 2 mg/dL
	7) HbA1c ≥ 7%
	8) QTcF > 450 msec for males or > 470 msec for females
	NOTE: In addition, subjects should be excluded if they have any other abnormal laboratory tests, vital sign results, or ECG findings which in the investigator's judgment are medically significant and that would impact the safety of the subject or the interpretation of the trial results. Tests with abnormal results should be repeated to ensure reproducibility of the abnormality before excluding a subject based on the criteria noted above.
18.	A history of dermatologic adverse reactions secondary to any drug exposure or anaphylaxis (or some type of systemic allergic reaction) to any substance.
19.	A history of allergic reaction or a known or suspected sensitivity to any substance that is
	contained in the IMP formulation.
20.	A history of prior exposure to centanafadine.

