- CT-6.1.6 Columbia-Suicide Severity Rating Scale Listing of Treatment Emergent Suicidal Ideation (Safety Analysis Set)
- CT-6.1.7 Columbia-Suicide Severity Rating Scale Listing of Treatment Emergent Serious Suicidal Ideation (Safety Analysis Set)
- CT-6.1.8 Columbia-Suicide Severity Rating Scale Listing of Worsening Suicidal Ideation (Safety Analysis Set)
- CT-6.2 Summary of Change from Baseline in Hamilton Anxiety Rating Scale Total Score (Safety Analysis Set)
- CT-6.3 Summary of Change from Baseline in Montgomery-Asberg Depression Rating Scale Total Score (Safety Analysis Set)
- CT-6.4 Summary of Study Medication Withdrawal Questionnaire (SMWQ) Total Score (Safety Analysis Set)
- CT-7.1 Extent of Exposure (Safety Analysis Set)
- CT-7.2 Number and Percentage of Subjects Receiving Study Medication and Mean and Range of Average Daily Dose (Safety Analysis Set)
- CT-8.1.1 Adverse Events (All Causalities) (Safety Analysis Set)
- CT-8.1.2 Adverse Events During the Single-Blind Placebo Run-in Period (All Causalities) (Safety Analysis Set)
- CT-8.2.1 Incidence of Treatment-Emergent Adverse Events by System Organ Class and MedDRA Preferred Term (Safety Analysis Set)
- CT-8.2.2 Incidence of Treatment-Emergent Adverse Events by System Organ Class, MedDRA Preferred Term and Severity (Safety Analysis Set)

- CT-8.2.3 Incidence of Treatment-Emergent Adverse Events of at Least 5% in Any Centanafadine Group and Greater Than Placebo by System Organ Class and MedDRA Preferred Term (Safety Analysis Set)
- CT-8.2.4 Incidence of Non-Serious Treatment-Emergent Adverse Events of at Least 5% in Any Centanafadine Group and Greater Than Placebo by System Organ Class and MedDRA Preferred Term (Safety Analysis Set)
- CT-8.2.5 Incidence of TREATMENT-EMERGENT ADVERSE Events of at Least 2% in Any Centanafadine Group and Greater Than Placebo by System Organ Class and MedDRA Preferred Term (Safety Analysis Set)
- CT-8.2.6 Incidence and Occurrence (Number of Events) of Serious Treatment-Emergent Adverse Events by System Organ Class and MedDRA Preferred Term (Safety Analysis Set)
- CT-8.2.7 Incidence and Occurrence (Number of Events) of Potentially Drug-Related Serious Treatment-Emergent Adverse Events by System Organ Class and MedDRA Preferred Term (Safety Analysis Set)
- CT-8.2.8 Incidence and Occurrence (Number of Events) of Non-Serious Treatment-Emergent Adverse Events by System Organ Class and MedDRA Preferred Term (Safety Analysis Set)

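### The SAP's count of emergent serious suicidal ideation leaves out subjects who were already rated 1-3 at the last pre-dose C-SSRS

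*SAP*

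**What the plan says.** SAP 9.7 sets out three ideation outcomes that are judged against baseline:

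- Emergence: "Emergence of suicidal ideation is defined as having no suicidal ideation at baseline and reporting any type of ideation during treatment".
- Emergence of serious ideation: "having no suicidal ideation at baseline and reporting serious suicidal ideation with score of 4 or 5" on the severity rating during treatment.
- Worsening: "Worsening of suicidal ideation is defined as having more severe in most severe suicidal ideation rating at post baseline than at baseline".

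The reference point is stated in the same section: "Baseline of C-SSRS data is defined as the last evaluable assessment prior to first IMP". Protocol Table 1.3-1 schedules the C-SSRS at screening and on Day -1, and protocol 8.7.5 uses the Since Last Visit form after screening. Baseline is therefore normally the Day -1 form.

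For ideation, the score-based part of protocol exclusion 15 is limited to a yes "on Questions 4 or 5 (over the last 6 months) on the suicidal ideation section of the Baseline/Screening version of the C-SSRS". Ratings 1-3 are not named, although other parts of the criterion (investigator judgment of risk, suicidal behavior) may exclude some of these subjects.

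SAP Appendix 4 plans a by-type ideation table (CT-6.1.3), a table of treatment-emergent behavior and ideation (CT-6.1.4), a "Listing of Treatment Emergent Serious Suicidal Ideation" (CT-6.1.7) and a listing of worsening ideation (CT-6.1.8).

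**The concern.** The word serious changes the event that is counted but not the baseline condition. A subject with a rating of 1-3 before dosing who reaches 4 or 5 on treatment has developed serious ideation that was not there before, yet does not meet the definition. Nor does the subject meet plain emergence of ideation, because some ideation was present at baseline.

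A reader looking for new serious ideation will go to the row and listing that carry that name. With 42 subjects planned per arm, such events are likely to be few, and one reclassified subject can turn a 1 into a 0 in that row.

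**Working it through.** No sample size, power or error rate is involved. The check applies the SAP 9.7 definitions to every combination of baseline and on-treatment rating.

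**Inputs**
- Ratings: SAP 9.7 names five ideation types, "wish to be dead, non-specific active suicidal thoughts, active suicidal ideation with any methods, active suicidal ideation with some intent" and then ideation with a specific plan. They are taken in that order as 1 to 5, with 0 for none. The numbering is inferred from the order and agrees with the SAP's use of 4 or 5 for serious.
- b = rating at the last pre-dose assessment; p = highest rating on treatment.
- CT-6.1.4 and CT-6.1.7 are assumed to use the SAP 9.7 definition, since no other is given and no table shells are shown.

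**Step 1. Count the transitions** (6 x 6 = 36 pairs of b and p)

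| Category | Rule | Pairs |
|---|---|---|
| Emergence of ideation | b = 0, p at least 1 | 5 |
| Emergence of serious ideation, per SAP | b = 0, p at least 4 | 2 |
| Worsening | p > b | 5 + 4 + 3 + 2 + 1 = 15 |
| Non-serious to serious | b at most 3, p at least 4 | 4 x 2 = 8 |

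The SAP row holds (0,4) and (0,5). It omits 8 - 2 = 6 pairs: (1,4), (1,5), (2,4), (2,5), (3,4), (3,5).

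**Step 2. See where the six go.** All six fail emergence of ideation, because b is at least 1. All six meet worsening, because p exceeds b. The 15 worsening pairs are 5 from b = 0, these 6, and 4 others: (1,2), (1,3), (2,3), (4,5). The worsening count therefore gives a step from 1 to 2 the same weight as a step from 3 to 5.

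**Step 3. Compare with the SAP's other onset rules.** For suicidal behavior and for ideation overall, what must be absent at baseline is the same thing that is counted later. For serious ideation it is not: any ideation must be absent, but only ratings 4-5 are counted. SAP Table 9.6-1 uses threshold crossing for QTc: new onset above 500 msec needs only that the baseline value was not above 500, so a subject at 480 msec before treatment still counts.

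**Step 4. Size.** The documents give no baseline ideation rate and no on-treatment risk, so the number affected cannot be computed. As an illustration on assumed inputs, let a share q of the 126 randomized subjects be rated 1-3 at the last pre-dose assessment, with a 5% risk of reaching 4-5. The expected number omitted is 126 x q x 0.05:
- q = 5%: 0.3 subjects
- q = 10%: 0.6 subjects
- q = 15%: 0.9 subjects

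That is fewer than one subject across the three arms.

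**The case against.** The strongest reply is that the scheme is deliberate. Emergence means de novo, and escalation of existing ideation has its own category and listing. The de novo row is meaningful and replacing it would lose information. That part stands, and it is a reason to add a row, not to redefine the present one. It does not explain why the serious row alone has a baseline condition wider than the event it counts.

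A reader might infer that these events go unreported. The documents do not support that. A subject who goes from 1-3 to 4-5 has an entry in CT-6.1.8 and should appear under the intent or plan type in CT-6.1.3. Because exclusion 15 bars a yes on Questions 4 or 5 at screening, few subjects should have a baseline of 4-5, so the on-treatment type 4 and 5 rows may come close to the wanted count. They are still not relative to baseline as titled, and one subject may be in both rows. CT-6.1.8 may show the individual ratings, but its layout is not given.

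A reader might also infer that anyone with ideation in the screening look-back is affected. That is too wide. A subject with no ideation on the Day -1 form has no baseline ideation and is counted. Entry also excludes a MADRS score of 18 or more, treatment for depression begun within 3 months before screening, and any lifetime suicidal behavior, which further narrows the group.

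Finally, the C-SSRS summaries are descriptive, and no test or decision rule depends on this row.

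**Conclusion.** The gap is real but minor. As written, the emergent serious-ideation row covers 2 of the 8 transitions from non-serious to serious. The other 6 are reported elsewhere, but in no count that isolates them. This rests on the inferred 1-5 numbering and on CT-6.1.4 and CT-6.1.7 following SAP 9.7.

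A claim that a large share of serious cases would be missing is not supported. With q from 5% to 15% and assumed risks of 5% for those rated 1-3 against 0.5% for those rated 0, the share is q x 0.05 / (q x 0.05 + (1 - q) x 0.005), or 34% to 64%. With equal risks the share is simply q, 5% to 15%. The result is driven by an assumed tenfold risk ratio that appears in neither document. What can be said is that the number of subjects is unknown and probably very small.

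**What to change.** In SAP 9.7, add an outcome for new serious ideation: a score of 4 or 5 during treatment with no score of 4 or 5 at baseline, using the existing C-SSRS baseline. This matches the form of the SAP's QTc new-onset rule. Give it a row in CT-6.1.4 and base listing CT-6.1.7 on it. Keep the present row, labelled as the subset with no ideation at baseline.

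The cost is a sentence of SAP text and one extra table row, with no new data or visits. Some subjects will be in both CT-6.1.7 and CT-6.1.8, but that is already so for those moving from 0 to 4 or 5, because worsening as defined includes them.

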9.8 Other Safety Data

Change from baseline in HAM-A total score, MADRS total score will be summarized by treatment group in descriptive statistics. SMWQ total score will be summarized by treatment group.

Classification of MHIs and Classification of Events Reported as findings in ESAM form will be summarized in frequencies and proportion by treatment group.

10 Rules for Scoring

10.1 Clinical Global Impression - Severity

The CGI-S is a standardized, clinician-administered global rating scale that measures disease severity on a 7-point scale. A higher score on the CGI-S represents a higher severity of disease. It is rated as: 1 = normal, not at all ill; 2 = borderline ill; 3 = mildly ill; 4 = moderately ill; 5 = markedly ill; 6 = severely ill; 7 = among the most extremely ill subjects.

10.2 Clinical Global Impression - Change

The CGI-C is a single-item, 7-point scale that requires the clinician to assess how much the subject's illness has improved or worsened relative to their baseline state at the beginning of treatment, rated as: 1 = very much improved; 2 = much improved; 3 = minimally improved; 4 = no change; 5 = minimally worse; 6 = much worse; or 7 = very much worse.

10.3 Yale-Brown Obsessive-Compulsive Scale Modified for Binge Eating

The Y-BOCS-BE is a clinician-rated scale that assesses obsession with binge eating thoughts and compulsiveness of binge eating behaviors. It can be divided into 2 subscales: obsessions (i.e., items 1-5) and compulsions (i.e., items 6-10). The Y-BOCS-BE is a 10-item scale, with each item rated from 0 (no symptoms) to 4 (extreme symptoms) and total scores ranging from 0 to 40, sub-scales scores ranging from 0 to 20. A score of 0 to 7 is sub-clinical; 8 to 15 is mild; 16 to 23 is moderate; 24 to 31 is severe; and 32 to 40 is extreme. Any missing item will lead total/sub-scale scores missing.

10.4 Eating Disorder Examination Questionnaire 7-Item Version

The EDE-Q7 is a brief version of the EDE-Q which comprises 7 items (to generate a global score and 3 subscales scores for dietary restraint, shape/weight overvaluation, and body dissatisfaction. Severity rating ranges from 0 to 6, where 0 represents absence of the feature and 6 represents an extreme degree. Frequency ratings range from 0 to 6 where 0= 'No days' or absence of the feature and 6= 'every day'. Global scores range from 0 to 42; dietary restraint subscales scores range from 0 to 18 (i.e., sum of scores from question 1 to 3), shape/weight overvaluation subscales scores range from 0 to 12 (i.e., sum of scores from question 4 to 5), and body dissatisfaction subscales scores range from 0 to 12(i.e., sum of scores from question 6 to 7). Any missing item will lead total/sub-scale scores missing.

10.5 Patient Global Impression - Severity

The PGI-S is a single-item self-report of the patient's severity of symptoms. Severity is rated on a 7-point scale as: 1 = no symptoms; 2 = minimal; 3 = mild; 4 = moderate; 5 = marked; 6 = severe; 7 = very severe.

10.6 Patient Global Impression - Change

The PGI-C is a single-item, 7-point patient self-report that requires the patient to assess how much his/her illness has improved or worsened relative to baseline, rated as: 1 = very much improved; 2 = much improved; 3 = minimally improved; 4 = no change; 5 = minimally worse; 6 = much worse; or 7 = very much worse.

10.7 36-Item Short-Form Health Survey

The 36-item Short-form Health Survey Version 2 (SF-36v2) is a patient-reported questionnaire with a standard recall period of 4 weeks which measures generic health-related quality of life on 2 broad domains, physical and mental composites, across eight health domain scales: physical functioning, pain, role physical, general health,

vitality/fatigue, social functioning role emotional, and mental health. The SF-36v2 uses norm-based scoring to generate scores on a scale of 0 to 100 where lower scores on PCS and MCS represent a lower health-related quality of life and a score of 50 references the normal US population. Those scores will be derived through QualityMetric's software¹³.

10.8 Hamilton Anxiety Rating Scale

The HAM-A consists of 14 items, each defined by a series of symptoms, and measures both psychic anxiety (mental agitation and psychological distress) and somatic anxiety (physical complaints related to anxiety). Each item is scored on a 5-point scale, ranging from 0 = not present to 4 = severe. HAM-A total scores range from 0 to 56. Any missing item will lead total scores missing.

10.9 Montgomery-Asberg Depression Rating Scale

The MADRS is a clinician-rated assessment of the subject's severity of depression. The measure contains 10 items that measure apparent and reported sadness, inner tension, reduced sleep and appetite, difficulty concentrating, lassitude, inability to feel, and pessimistic and suicidal thoughts. Each item is scored in a range of 0 to 6 points, with higher scores indicating increased depressive symptoms. MADRS total scores range from 0 to 60. Any missing item will lead total scores missing.

10.10 Study Medication Withdrawal Questionnaire

The SMWQ is a questionnaire to assess withdrawal symptoms that will be assessed at week 8/ET and 7 days after the last dose of IMP in the follow-up period. The SMWQ is a modification of the Amphetamine Withdrawal Questionnaire in which the terms "amphetamines and methamphetamine" are replaced with the term "the study medication." This questionnaire consists of 10 questions. Each is scored in 0 = Not at all, 1 = Very little, 2 = A little, 3 = Quite a lot, 4 = Very much. The SMWQ total score ranges from 0 to 40. Any missing item will lead total scores missing.

10.11 Columbia-Suicide Severity Rating Scale (C-SSRS)

Suicidality will be monitored during the trial using the C-SSRS. The C-SSRS is a semistructured interview that captures the occurrence, severity, and frequency of suiciderelated thoughts and behaviors during the assessment period. The interview includes definitions and suggested questions to solicit the type of information needed to determine if a suicide-related thought or behavior has occurred.

The C-SSRS has a "Screening/Baseline" version, which will be completed at screening and a "Since Last Visit" version that will be completed at all scheduled visits (including the ET visit, if applicable). There are a maximum of 19 items to be completed: 7

required, 10 potential additional items if there is a positive response to a required item, and 2 items for suicide/suicide behavior present during the interview. The C-SSRS uses dichotomous scales (i.e., yes or no), Likert scales, and text or narrative to further describe the thoughts or behaviors.

11 Pharmacokinetic Analyses

Sparse PK samples will be evaluated to confirm compliance with dosing. Concentrations will be listed in the bioanalytical report.

12 Pharmacodynamic Analyses

No pharmacogenomic analyses is planned.

13 Pharmacogenomic Analyses

No pharmacogenomic analyses is planned.

14 Interim Analysis

No interim analyses is planned.

15 Changes in the Planned Analyses

Trial center will not be included in ANCOVA model for analyses of change from baseline in fasting triglycerides and total cholesterol at Week 8/ET.

16 References

- 3. Little RJA. Pattern-mixture models for multivariate incomplete data. J Am Stat Assoc. 1993; 88:125-34.
- 4. Little RJA. Modeling the drop-out mechanism in repeated measures studies. J Am Stat Assoc. 1995; 90:1112-21.

